#### **5. Trial Procedures**

Investigators will record data onto web-based forms or paper forms and send the data to the CEQUEL office either electronically or by fax. The trial office will then instruct the trial pharmacy to post the allocated medicines to the address nominated by the participant (see sections 6.7.3. and 6.7.4.)

##### **5.1. Entry to the run-in phase**

Patients will be informed about the trial and provided with a copy of the Participant Information Sheet by their psychiatrist (or, at the request of the psychiatrist and with the patient's permission, by a member of the CEQUEL team) during a routine appointment. They will be given the opportunity to ask questions and as much time as they require to decide about participation. For patients who are willing to take part, informed consent will be obtained by their psychiatrist or, with his/her agreement, by a trial investigator.

*5.1.1. Pre-treatment checks:* Investigators will be prompted to arrange the investigations recommended by the NICE guidelines on bipolar disorder (NICE, 2006) when initiating treatment with quetiapine.

*5.1.2. Data to be collected on entry to run-in phase:*

##### Demographics and contact details:

- participant name (title, given name and family name), date of birth, gender, ethnicity
- participant address, mobile phone number, other daytime telephone number, email address
- GP name, surgery address

##### Clinical information:

- check eligibility for run-in phase (see section 4.1.)
- diagnosis – bipolar I disorder or bipolar II disorder (based on DSM-IV criteria for a hypomanic or manic episode)
- current use of vitamin supplements containing folic acid

##### Blood test:

A blood sample will be taken to check:

- baseline folate and B12 (cobalamin and holotranscobalamin) and homocysteine levels\*
- single nucleotide polymorphisms MTHFR C677T; COMT Val158Met; FOLH1 T484C

- \* See section 7.4. for procedures to be followed if a participant is found to be B12 deficient.

At the end of the appointment, quetiapine will be prescribed according to local practice and data forms will be submitted to the CEQUEL Office electronically or by fax.

Self-reporting by SMS, webform or hardcopy will be requested after the appointment

- QIDS-SR16
- ASRMS
- Quality of Life Questionnaire

**5.2. Entry to the randomised phase**

Following successful completion of the run-in phase participants will be invited to attend a randomisation appointment:

*5.2.1. Initiation and monitoring:* Investigators will be prompted to follow guidelines on initiation and monitoring for lamotrigine and folic acid including providing information to women on the use of oral contraceptives whilst taking lamotrigine as outlined in the Summary of Product Characteristics.

*5.2.2. Data to be collected at the randomisation visit:*

Clinical Information

- check eligibility for randomised phase (see section 4.2.)
- dose of quetiapine to be continued
- comorbid substance abuse, anxiety disorder, eating disorder or psychotic symptoms# (according to DSM-IV criteria)
- previous treatment for this episode
- psychotropic medicines taken in the 30 days prior to screening
- psychotropic medicines to be continued in trial
- DSH history

# Note: patients who have a primary diagnosis of schizophrenia are not eligible for CEQUEL

Participant completed in clinic

- QIDS-SR16 \*
- ASRM
- Quality of Life Questionnaire

\* to be scored by investigator during appointment to check eligibility

Drug supply

- Address for medicines to be sent to (if different from home address)

Randomisation will be arranged with full allocation concealment via the electronic Case Report Form (CRF). Investigators who do not have internet access will fax the randomisation forms to the CEQUEL Office where random allocation will be arranged (see section 3.2.3.).

At the end of the appointment, quetiapine will be prescribed according to local practice, Lamotrigine/placebo and folic acid/placebo will be prescribed using electronic or paper trial prescription forms which will be submitted to the CEQUEL Office together with the data forms electronically or by fax.

**5.3. Follow-up visit 1 (12 weeks)**

The first follow-up visit should be scheduled for 12 weeks post-randomisation (+/- 14 days).

### 5.3.1. Data to be collected at follow-up visit 1:

#### Clinical Information

- details of any changes to dose of quetiapine
- dose of lamotrigine/placebo established post-randomisation
- details of any subsequent changes to dose of lamotrigine
- adherence to lamotrigine/placebo and folic acid/placebo and quetiapine
- details of any admissions to hospital
- details of any new treatments for emergent manic or depressive symptoms
- details of any new SAEs or non-serious AEs that are subject to routine reporting (see section 8.2.3.)
- DSH.

#### Blood test:

A blood sample will be taken to check:

- folate, B12 (cobalamin and holotranscobalamin) and homocysteine levels.

### 5.4. Follow-up form (22 weeks)

The investigator will be asked to provide follow-up data and to confirm doses of allocated treatment 22 weeks after randomisation. Provided that routine follow-up is continuing, there will be no need for the participant to be present when these forms are completed.

#### 5.4.1. Data to be requested at 22 weeks:

##### Clinical Information

- details of any changes to dose of quetiapine
- details of any changes to dose of lamotrigine
- adherence to lamotrigine/placebo and folic acid/placebo and quetiapine
- details of any admissions to hospital
- details of any new treatments for emergent manic or depressive symptoms
- details of any new SAEs or non-serious AEs that are subject to routine reporting (see section 8.2.3.)
- DSH

### 5.5. Follow-up Visit 2 (52 weeks)

The second follow-up visit should be scheduled for 52 weeks post-randomisation (+/- 2 weeks).

#### 5.5.1. Data to be collected at follow-up visit 2:

##### Clinical Information

- details of any changes to dose of quetiapine
- details of any changes to dose of lamotrigine
- adherence to lamotrigine/placebo and folic acid/placebo and quetiapine
- details of any admissions to hospital
- details of any new treatments for emergent manic or depressive symptoms
- details of any new SAEs or non-serious AEs that are subject to routine reporting (see section 8.2.3.)
- DSH

### 5.6. Participant reported outcomes

Participants will be asked to complete the QIDS-SR16 and the ASRM rating scales by SMS (or webform or hardcopy) once a week for the duration of the randomised phase (see section 5.7. for procedures). In addition to this, participants will be asked, once a month, to complete the EuroQol scale and report contact with health and

social care professionals and initiation of new treatment for mood symptoms. If either contact or new treatment is reported, a member of the CEQUEL team will phone or email the participant to collect further information.

#### **5.7. SMS (or webform) self-reporting of mood by participants**

Participants will be given credit-card sized version of the QIDS-SR16 and the ASRM and EuroQol (EQ-5D) rating scales. For each scale an SMS prompt will be sent to participants' mobile phones when the rating is due. The SMS responses will consist of a single letter to identify the scale followed by a series of numbers corresponding to participants' ratings of the individual items on the scale.

Replies received by the administering computer system will be automatically checked for transcription errors (i.e. too many or too few digits or numbers that are not valid for the scale). If any errors are detected, the system will notify the participant, via an SMS message, and ask him/her to re-send his/her answers.

If a reply is not received, the administering computer system will generate daily prompts for two days unless or until a reply is received.

Participants who do not have access to a mobile phone or who do not want to complete ratings by SMS will be able to complete ratings by webform with weekly prompts as for SMS ratings. Participants unwilling/unable to use SMS or webform will be provided with paper copies of the two scales and freepost envelopes in which to return them to the CEQUEL office.

#### **5.8. Emergency procedures for unmasking treatment allocation**

Investigators and participants will be provided with the telephone number for an on-call member of the trial team. This number will operate 24 hours a day 7 days a week and can be used to request unblinding of one or both treatment allocations in the event of a medical emergency. Procedures will be put in place to verify the identity of the participant and caller and the decision on whether to reveal the allocation will be based on a set of criteria for judging clinical need.

#### **5.9. Unblinding at the end of the trial**

Premature disclosure of allocation risks introducing bias and invalidating the trial results. Masking of treatment allocation will therefore be maintained during the course of the trial unless an adverse event arises that clinically requires disclosure. If a participant formally (in writing to the CEQUEL office) requests disclosure of their treatment allocation, this will be made available to them alone after they have left the trial or at 12 months post-randomisation (whichever is the longer).

#### **5.10. Post-trial follow-up**

Following completion of the randomised phase or withdrawal from trial follow-up, participants will be contacted by telephone between 7 and 10 days after final contact to update the status of any continuing adverse events and to record any new events. Further follow-up by visit or telephone call will be arranged as required.

**5.11. Duration of trial**

The active run-in phase will last for 7 to 14 days and the randomised phase for 52 weeks.

**5.12. Definition of the end of trial**

The end of the trial will be the date of the last visit of the last participant.

**5.13. Discontinuation criteria and procedures**

In accordance with the current revision of the Declaration of Helsinki (amended October 2000, with additional footnotes added 2002 and 2004), a participant has the right to stop trial treatment and to withdraw from the trial at any time and for any reason, without prejudice to his or her future medical care by the physician or at the institution, and is not obliged to give his or her reasons for doing so.

The investigator may withdraw a participant from trial treatment at any time in the interests of the participant's health and well-being or for administrative reasons. The date and reason for termination of treatment will be recorded. Trial follow-up (including weekly self-reports of mood) will continue after treatment has been withdrawn unless the participant withdraws consent.

If a participant withdraws from the active run-in phase or withdraws from follow-up during the randomised phase, the date and reason for withdrawal will be recorded in the CRF.

**6. Trial Treatments****6.1. Provision of trial treatments**

Investigators will be responsible for arranging the supply of quetiapine and for using trial prescription forms to prescribe both lamotrigine/placebo and folic acid/placebo according to the dose regimens outlined in sections 6.2 to 6.4. (Recommended rescue medicines are recorded in section 6.5.2.)

Participants will be advised to contact the investigator to report any unexpected occurrence or effect that they think might be related to quetiapine, lamotrigine or folic acid.

**6.2. Standard treatment – quetiapine**

At the start of the active run-in phase, all participants will be prescribed oral quetiapine once daily as standard first-line treatment for bipolar depression (NICE, 2006). This will be prescribed by the investigator or the participant's GP according to local practice. Investigators will be encouraged to request that 25mg tablets be dispensed until the dose is established to allow rapid changes of dose.

The recommended titration schedule to a target dose of 300mg is shown in Table 1 but a lower starting dose and/or slower titration may be used. If the participant is not able to tolerate 300mg/day, the maximum tolerated dose should be prescribed. Quetiapine may be given twice daily if this is considered to be clinically appropriate. Participants who are not able to tolerate at least 150 mg/day are not eligible for randomisation.

The dose of quetiapine should not be altered within 3 days of randomisation to ensure that the tolerability of the proposed dose has been established.

Prescription of quetiapine at the dose established during the run-in phase should continue throughout the randomised phase unless there are clinical reasons to stop or the participant withdraws consent. Changes to the dose of quetiapine post-randomisation will be considered to be protocol non-compliant. When this does occur the reason for the change will be recorded.

*Table 1: Recommended titration schedule for quetiapine*

	Days 1 & 2	Days 3 & 4	Day 5	Days 7 to 52
Daily dose	50mg	100mg	200mg	300mg →

### 6.3. Lamotrigine (or matching placebo according to allocation)

The recommended dose of lamotrigine will vary according to whether participants are on concurrent valproate and, for women, combined oral contraceptives – see Table 2 for recommended and minimum doses and sections 6.3.1. to 6.3.3 for titration schedules.

**Table 2 Recommended doses (and minimum doses)**

Concurrent valproate	Concurrent combined oral contraceptives	Recommended (minimum) dose (mg/day)	Section
No	No	200 (100)	6.3.1.
Yes	No	100 (50)	6.3.2.
Yes	Yes	100 (50)	6.3.2.
No	Yes	400 (200)	6.3.3.

The investigator will explain the dosing schedule to the participant and the pharmacy will provide a chart showing the daily dose of lamotrigine/placebo for each week during the period when the lamotrigine dose is being titrated.

*6.3.1. Titration schedule for participants not taking valproate or combined oral contraceptives:* The initial dose of lamotrigine (or placebo) following randomisation will be 25mg/day increasing to 200mg/day after 6 weeks. For participants who cannot tolerate the 200mg/day, the highest dose that can be tolerated should be prescribed with a minimum recommended dose of 100mg/day.

*Table 3: Titration schedule for lamotrigine for participants not on valproate or combined oral contraceptives*

Target dose	Weeks 1 & 2	Weeks 3 & 4	Weeks 5 & 6	Weeks 7 to 52
200mg/day	25mg	50mg	100mg	200mg →

*6.3.2. Titration schedule for participants also taking valproate (regardless of whether they are also taking combined oral contraceptives):* The initial doses of lamotrigine or placebo will be 25mg every other day increasing to 100mg after 6 weeks. For participants who cannot tolerate the 100mg/day, the highest dose that can be tolerated should be prescribed with a minimum recommended dose of 50mg/day.

*Table 4: Titration schedule for lamotrigine for participants also taking valproate (+/- combined oral contraceptives)*

Target dose	Weeks 1 & 2	Weeks 3 & 4	Weeks 5 & 6	Weeks 7 – 52
100mg/day	25mg every other day	25mg	50mg	100mg→

**6.3.3. Titration schedule for women also taking combined oral contraceptives but not valproate:** The initial dose of lamotrigine or placebo will be 25mg/day increasing to 400mg/day after 7 weeks. If this is not tolerated (including during pill-free weeks) the dose can be reduced to 200mg.

*Table 5: Titration schedule for lamotrigine for women also taking combined oral contraceptives but not valproate .*

Target dose	Weeks 1 - 2	Weeks 3 - 4	Week 5	Week 6	Weeks 7	Week 8
400mg/day	25mg	50mg	100mg	200mg	300mg	400mg →

**Note:** Women should be advised to tell the investigator if they stop oral contraceptives so that the doses of lamotrigine can be adjusted.

#### **6.4. Folic acid (or matching placebo according to allocation)**

The dose (to be taken orally) will be 500µg/day as a single daily dose for the full 52 weeks of the randomised phase.

**6.4.1. B12 deficiency:** The results of the blood sample taken during the run-in phase should be available to the co-ordinating centre within 8 weeks of the participant starting treatment with folic acid. If the results indicate B12 deficiency the investigator will be informed immediately so that B12 supplements can be given. The blinding will not be broken unless it is clinically mandatory to do so (see section 5.8).

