- ii) There is also some evidence for a potential interaction between the catechol-o-methyltransferase (COMT) enzyme genotype and response to treatment with folic acid. The COMT gene has a functional SNP (Val158Met) which alters enzyme activity and Val158 homozygotes have been found to have significantly higher levels of homocysteine than Met158 carriers, The COMT effect was independent of, and additive with, the MTHFR 677TT effect (Tunbridge et al. in press).
- iii) Folate hydrolase 1 (FOLH1) facilitates the transfer of dietary folate into the body. Its activity is modulated by a functional variant in its sequence (T484C): the 484T variant has higher activity than the 484C form. Accordingly, the effects of folate supplementation on homocysteine levels and depressive symptoms may be more pronounced in 484TT homozygotes, compared with 484C carriers (Roffman et al 2013).

CEQUEL will investigate the hypothesis that there will be an interaction between folic acid treatment and genotype at these loci. We predict a greater reduction in homocysteine levels – and also depressive symptoms - in 677TT and Val158 homozygotes. In addition, we hypothesise that the impact of folate on biochemical measures (and depressive symptoms) will be more pronounced in FOLH1 484TT homozygotes.

**1.3.6. B12 status:** There is growing evidence of interactions between vitamin B12 status and folate status, with adverse effects of high folate in those with low B12 status. We will also look at baseline B12 status in relation to outcome measures by analysis of total cobalamin and holotranscobalamin [Refsum, 2006b].

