## **7. Blood Tests**

### **7.1. Timing of blood samples**

Participants will be asked to give a blood sample (approximately 10ml.) at the screening appointment and again at the 12-week follow-up appointment.

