## 7.2. Obtaining blood samples

Investigators will be provided with blood collection tubes that can be used to collect samples for homocysteine assay and serum tests. Investigators will also be provided with packaging so that the samples can be mailed to the CEQUEL office. At the screening appointment the investigator should either take the blood samples or arrange for the samples to be taken before randomisation.

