## 7.3. Storage and analysis of blood samples

On receipt at the CEQUEL office, samples will be taken to the Department of Neurosciences where they will be centrifuged. The serum will be sent to the Department of Physiology Anatomy and Genetics where the biochemical tests will be performed. The test results will be available within 2 months of receipt of the sample. The remainder of the samples will be retained in Neurosciences for genotyping.

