## 7.4. B12 deficiency

In the unlikely event that a participant is found to be B12 deficient (defined as serum level below 150pmol/L), the investigator will be informed and advised about the need for the participant to be prescribed B12 supplementation. No other blood test results will be reported to investigators.

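### The baseline B12 result may arrive up to 8 weeks after folic acid/placebo starts, although the blood is already drawn, so the supplementation safeguard can act late (minor safety point)

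*Protocol*

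**What the plan says.** Section 1.3.6 of the protocol describes an interaction between B12 and folate status, "with adverse effects of high folate in those with low B12 status", and plans to relate baseline B12 to outcome.

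Section 7.1 asks for blood "at the screening appointment and again at the 12-week follow-up appointment". Section 7.2 adds that the investigator "should either take the blood samples or arrange for the samples to be taken before randomisation". On processing, section 7.3 states: "The serum will be sent to the Department of Physiology Anatomy and Genetics where the biochemical tests will be performed", and then: "The test results will be available within 2 months of receipt of the sample". That single turnaround covers all the biochemical tests.

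Section 6.4.1 then says that the result of the run-in sample "should be available to the co-ordinating centre within 8 weeks of the participant starting treatment with folic acid". If it indicates deficiency, the investigator is to be informed immediately so that B12 can be supplemented, and the blind is kept unless breaking it is clinically mandatory. Section 7.4 sets the threshold at a serum level below 150 pmol/L and opens with "In the unlikely event that a participant is found to be B12 deficient".

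Under section 6.7.3 the folic acid/placebo is posted once the participant has been randomised. The additional criteria for the randomised phase in section 4.2 do not include a B12 result.

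**The concern.** The protocol names a hazard, chooses a safeguard against it, and then allows the safeguard to act well after exposure has begun. The promise to inform the investigator immediately takes effect only once a result exists, and 6.4.1 accepts a result as late as 8 weeks into treatment. The information needed is in a tube collected before the first dose. The delay therefore comes from the order and pace of processing, not from any missing sample.

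At stake is the safety of a small group: participants whose deficiency nobody yet knows about and who are allocated to active folic acid at 500 µg/day. Until the result arrives, nothing in the protocol would lead to their being supplemented unless a clinician happened to test them for another reason.

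**Working it through.** **Inputs**
- Limit for the B12 result: 8 weeks from the start of folic acid/placebo (6.4.1) = 8 × 7 = 56 days.
- Laboratory turnaround: 2 months from receipt (7.3). Two consecutive calendar months are 59 to 62 days.
- Trial entry to randomisation: 7 to 14 days (3.2.3), with extensions possible on request.
- Assumptions: the sample is received at trial entry, the first dose is taken at randomisation, and the postal times of sample and medicine cancel.

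**Reproducing the plan's own figure**

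Latest result after first dose = turnaround − days from receipt to first dose.
- Earliest of these latest times: 59 − 14 = 45 days = 45/7 = 6.4 weeks.
- Latest: 62 − 7 = 55 days = 55/7 = 7.9 weeks.

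Both lie inside 56 days. The 8-week limit is thus what a 2-month turnaround gives for a sample taken at screening with a normal run-in. Both sections set upper limits, so any earlier result also complies. A longer run-in would shorten the interval.

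**Does anything else close the gap?**

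| Provision | Does it catch an unrecognised deficiency? |
|---|---|
| 4.1.2, exclusion for definite contraindications to folic acid | No. It works only on what is already known. |
| 4.2, criteria for the randomised phase | No. No B12 result is required. |
| 5.2.1, "Investigators will be prompted to follow guidelines on initiation and monitoring for lamotrigine and folic acid" | Not shown. No B12 check is mentioned. |
| 5.8, emergency unblinding | No. It responds to an emergency and does not detect deficiency. |
| 7.3, turnaround | No. B12 is not separated from the other biochemical tests. |

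**What assaying B12 first could achieve**

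If the B12 result is ready T days after receipt, the unsupplemented time is T minus the run-in days, or 0 if that is negative. The protocol does not give T, so these values are illustrations only:
- T = 14: 14 − 14 = 0 to 14 − 7 = 7 days.
- T = 28: 28 − 14 = 14 to 28 − 7 = 21 days.

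Both compare with a permitted maximum of 56 days now.

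**The case against.** The strongest reply is that this is an openly stated operational choice. Section 6.4.1 sets out the timing, the action and the blinding rule, 7.4 gives the threshold, and nothing is misstated. That stands: the point is about a choice that could be improved cheaply, not about an error.

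The reply can add that harm is not shown. Section 1.3.6 speaks of high folate and does not say that 500 µg/day for up to 8 weeks is dangerous. This also stands, and it is why the point carries little weight. There is some general cover too: 3.2 expects investigators to carry out clinically indicated investigations, and 5.2.1 prompts them to follow folic acid guidance. Neither is shown to find a silent deficiency.

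Two stronger readings are tempting and should be resisted.

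- A reader might infer that 7.3 lets the result come later than 8 weeks when blood is drawn just before randomisation, or when a patient already on quetiapine enters the randomised phase directly. The documents do not support this. Section 6.4.1 is the rule specific to B12 and caps the delay at 8 weeks. Section 7.3 is a general turnaround, and both can be met together. Any apparent excess would be a matter of days and would depend on reading 2 months as calendar months and ignoring the post in both directions.
- A reader might infer a contradiction with 4.1.2. There is none, because an exclusion for definite contraindications cannot apply to a condition not yet recognised.

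**Conclusion.** The concern holds as a minor timing weakness. The protocol permits up to 8 weeks between the first folic acid/placebo dose and the baseline B12 result, and no other provision protects a participant with unrecognised deficiency during that time. Eight weeks is 8/52 = 15% of the randomised phase, and it is a ceiling, not a forecast.

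Only participants allocated to active folic acid are exposed. The number affected cannot be given, because the protocol states no prevalence and describes deficiency as unlikely. The size of any harm cannot be given either. The conclusion rests only on the stated limit in 6.4.1, the blood draw before randomisation, and the absence of any rule that the first dose waits for the result. It has no bearing on sample size, power or the primary analysis.

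**What to change.** In 6.4.1 and 7.3, state that serum B12 is assayed first on receipt of the baseline sample and is not held for the 2-month turnaround of the other biochemical tests. State also that a result below 150 pmol/L is reported to the investigator at once, if possible before the first dose of folic acid/placebo. Leave randomisation, eligibility, the other assays and blinding unchanged. A baseline B12 value does not reveal the allocation.

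No new visit or sample is needed. The costs are modest:
- B12 assay runs become smaller and more frequent. Samples are posted to the trial office and pass through two departments (7.2, 7.3), and the protocol does not say how fast that chain can report. The wording should therefore not promise a fixed number of days unless the laboratory confirms one.
- The few deficient participants would be supplemented earlier, before the 12-week outcome. This slightly affects the low-B12 contrast in secondary question 5 (section 2.2). Dates of supplementation should be recorded so that the analysis can take account of them.
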